### 3.0 STUDY HYPOTHESES

The prolongation of analgesia provided by adding liposomal bupivacaine to bupivacaine is non-inferior to Bupivacaine with preservative free dexamethasone.

### 4.0 STUDY DESIGN

#### 4.1 Endpoints

##### 4.1.1 Primary Endpoint

- The primary outcome is average NRS pain score at rest over 72 hours (average of 3 24-hour time point [24, 48, 72 hours]).

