##### 4.1.2 Secondary Endpoints

- 1. NRS pain scores at rest on PACU, POD1, POD2, POD3, POD4, POD7
- 2. NRS pain scores with movement in PACU, POD 1, POD2, POD3, POD4, POD7
- 3. Brief Pain Inventory short-form in PACU, POD1, POD2, POD3, POD4, POD7
- 4. Opioid consumption in PACU, POD1, POD2, POD3, POD4, POD 7
- 5. Patient Satisfaction with pain treatment in PACU, POD 1, POD 2, POD 3, POD 4, POD 7
- 6. Duration of analgesic block via RA phone call 24, 48, 72 hours after block placement (or longer if block continues): Patient's will be asked "Since being discharged, when did you first take an analgesic medication for shoulder pain?" and "When did your pain relief from the block completely wore off?"
- 7. Sensory resolution in PACU, POD1, POD2, POD3, POD4, POD7 (full resolution of block will be reported by the patient via RA phone call 24, 48, 72 hours after block placement or longer if duration continues, "When did your numbness completely resolve and returned to normal?", will likely be until POD 1, but would continue until block resolution)
- 8. Motor block resolution in PACU, POD1, POD2, POD3, POD4, POD7 (full resolution of block will be reported by the patient via RA phone call 24, 48, 72 hours after block placement or longer if block continues, "When did your arm or hand weakness resolve and returned to normal?", will likely be until POD 1, but would continue until block resolution)
- 9. Success of interscalene block: C5 Dermatome distribution will be assessed in the PACU by the anesthesiologist (co-i). Alcohol swab test (2-normal cold sensation, 1-diminished/dull, 0-absence of cold sensation). Motor test: hand grip (normal-2, weak-1, absent-0)
- 10. Adverse effects: sensory-motor deficits: incidence of paresthesia / neuropraxia: persistent tingling, numbness on POD7, if patient reports persistent neuropraxia after POD7, will follow up on POD14. If neuropraxia persists, will notify attending anesthesiologist and continue to

follow until postoperative neurological symptoms (PONS) resolve. On POD 7, patients will be asked “on the side where surgery was performed, do you have any numbness, tingling, or weakness in the hand or fingers?”

- 11. If the response to continued numbness/tingling in fingers on POD7 is yes, adverse effects will be asked on POD 14.
- 12. Incidence of ISB related side effects: Horner’s syndrome, hoarseness, hiccups, dyspnea in PACU, POD1-4,7

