**7.0 STATISTICAL ANALYSIS**

- Proposed analysis: T-Test
- Interim analysis planned: Yes, at the 50% mark of 56 patients
- Alpha level: 0.05
- Beta or power level: 0.8
- Primary outcome variable estimate (mean +/- s.d. for continuous outcome, frequency/percentage for categorical variable): Mean difference of 1.3 +/- 1.0
- Number of groups being compared: 2
- Effect size or change expected between groups: Noninferior margin of 1.3
- Resulting number per group: 51
- Total sample size required: 102 + 10% (for attrition/withdrawal) = 112

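### The primary endpoint averages three daily scores and is compared by t-test, with no rule for a patient who has only one or two of them; a repeated-measures estimate of the same three-day mean would use all the data.

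*Combined protocol and SAP*

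**What the plan says.** Section 4.1.1 (and Section 2.0) defines the primary outcome as the "average NRS pain score at rest over 72 hours (average of 3 24-hour time point [24, 48, 72 hours"). Section 7.0 and the synopsis give the analysis in one line: "Proposed analysis: T-Test". The other relevant entries in Section 7.0 are "Alpha level: 0.05", "Beta or power level: 0.8", "Noninferior margin of 1.3", "Mean difference of 1.3 +/- 1.0" and "Total sample size required: 102 + 10% (for attrition/withdrawal) = 112".

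Patients are outpatients, so the three scores are normally obtained after discharge. Section 6.3 lists NRS on each of POD 1, 2 and 3. Section 4.1.2 describes contact "via RA phone call 24, 48, 72 hours after block placement", but for block duration and resolution. That the primary NRS is taken in those same calls is a reasonable inference, not a statement in the text.

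The documents give no analysis set, minimum number of scores, imputation rule, repeated-measures model or expected rate of missed assessments. The allowance of 10% is for attrition and withdrawal; missed assessments are not mentioned.

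**The concern.** A t-test on a three-day average needs a complete average for each patient. Someone who answers at 24 and 72 h but not at 48 h has no average of three, so the literal reading discards a randomised patient with two valid scores. If missing a call is related to pain, sedation or a persisting block, and these differ by arm, dropping such patients lets selection into the comparison.

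The common workaround is to average the scores that exist. A patient last reached at 24 h is then scored close to block offset only (the introduction cites prolongation of up to 22 hours with dexamethasone), while a patient missed at 24 h is scored on later days only. If the pattern of missed calls differs by arm, the arm difference moves without any treatment effect.

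The claim is non-inferiority, so a bias that shrinks a real disadvantage favours a positive conclusion. With no rule written down, the choice falls to whoever analyses the data, possibly after seeing them, and an interim analysis is planned at 56 patients.

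**Working it through.** **Inputs from Section 7.0:** margin 1.3; SD read as 1.0; alpha 0.05 (sidedness not stated); power 0.8; 51 per group, 102 in total, 112 after the allowance. **Assumed, because the documents give none:** miss rate per call p, clustering of misses, withdrawal rate w, within-patient correlation of scores, and the difference in pain between days.

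**1. The plan's own figures.** The allowance reproduces: 102 × 1.10 = 112.2, stated as 112. That leaves 112 − 102 = 10 spare patients, or 10/112 = 8.93%. The 51 per group does not reproduce: 2 × (1.960 + 0.842)² × (1.0/1.3)² = 9.3, so about 10 per group. That mismatch is a separate matter, but it bears on step 4.

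**2. Patients without a full average.** With independent misses the share is 1 − (1 − p)³.

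| p per call | incomplete | complete of 112 |
|---|---|---|
| 2% | 5.9% | about 105 |
| 5% | 14.3% | about 96 |
| 10% | 27.1% | about 82 |

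Almost all of these patients have some data: at p = 10% only 0.10³ = 0.1% miss all three calls.

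**3. When the spare patients run out, if incomplete patients are dropped.** With no withdrawals and independent misses, (1 − p)³ = 102/112 = 0.9107, so p = 3.07%. Clustering of misses within patients raises this (beta-binomial, correlation of misses r):

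| r | 0 | 0.2 | 0.5 | 0.8 | 1 |
|---|---|---|---|---|---|
| break-even p | 3.1% | 3.7% | 5.0% | 6.9% | 8.9% |

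Withdrawals lower it. Solving (1 − w)(1 − p)³ = 102/112 with independent misses gives p = 2.4% at w = 2%, 1.4% at 5% and 0.3% at 8%.

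**4. Does that cost power?** Power ≈ Φ(1.3 / (SD × √(2/n)) − 1.96), true difference 0. With SD 1.0 and n = 40 per group: 1.3/√0.05 = 5.81, 5.81 − 1.96 = 3.85, power above 99.9%. The loss matters only if the SD is much larger. At SD 2.34, the value that would justify 51 per group at two-sided 0.05, power is 80.0% at 51, 77.6% at 48 and 69.9% at 40 per group. The documents do not state such an SD.

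**5. Shift from averaging over different days.** Assume both later days run 2 points above the 24 h score x. The full mean is x + 4/3.
- Only the 24 h call missed: available mean x + 2, error +2/3. With 10 percentage points more such patients in one arm: 0.10 × 2/3 = 0.07.
- Lost after 24 h: available mean x, error −4/3. With 10 percentage points more in one arm: 0.10 × 4/3 = 0.13.

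Against the margin these are 0.07/1.3 = 5% and 0.13/1.3 = 10%.

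**6. Precision.** Assume independent random misses, compound symmetry and correlation ρ of 0.4 to 0.6. The complete-case variance of the three-day mean is proportional to [(1 + 2ρ)/3]/(1 − p)³. The all-data variance is c′I⁻¹c, where c = (1/3, 1/3, 1/3) and I sums, over the patterns of observed scores, the probability of the pattern times the inverse covariance of the observed scores.

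| p | complete-case / all-data variance | reduction | available-score average / model |
|---|---|---|---|
| 5% | 1.14–1.15 | 12–13% | 1.002–1.005 |
| 10% | 1.31–1.33 | 24–25% | 1.004–1.010 |

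The last column shows that plain averaging of available scores comes within about 1% of the model's variance when misses are random and day means are equal. The gain comes from keeping partial patients, not from the model as such.

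**The case against.** A t-test on a per-patient summary is a standard and valid analysis, and the plan is silent rather than committed to dropping anyone; an imputation or averaging rule could still be written. That stands, and it makes this an omission to close, not an invalid test. A one-line rule to average available scores would recover nearly all the precision. That also stands; what the model adds is that it targets the same three days for every patient, and the bias it removes is small in the examples above.

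Four stronger readings are tempting and are not supported.
- **The allowance is exhausted at about 3% missed calls.** This needs independent misses, complete-case analysis and no withdrawals, none of which the documents give. With no withdrawals the range is 3.1% to 8.9%, and if available scores are averaged almost nobody is lost.
- **The trial would be underpowered.** On the stated margin and SD it would not.
- **Averaging available scores is worse than dropping patients.** Neither bias can be sized from the documents, so the ranking is not shown.
- **A missed call ends follow-up.** No passage says so; Section 6.3 lists each day separately.

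**Conclusion.** The point holds as a gap in the primary analysis that should be closed before the data are seen. The documents define a three-score average and a one-number test, and leave the patient with one or two scores without a rule. The harm is possible selection bias and the loss of usable data from randomised patients, not loss of power.

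Its size depends on a miss rate that the documents do not give. At an assumed 5% to 10% per call with independent misses, 14% to 27% of patients would lack a full average, and using all scores would lower the variance by 12–13% to 24–25%. The day-mix shift of 0.07 to 0.13 points is illustrative, resting on an assumed 2-point difference between days and an imbalance of 10 percentage points between arms. It would not by itself overturn a clear result against a margin of 1.3, but could matter for a confidence limit close to it.

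**What to change.** In Section 7.0 and the synopsis:
- Keep the estimand: mean NRS at rest over 24, 48 and 72 h.
- Estimate it with a repeated-measures model with arm, time, arm-by-time and unstructured covariance, including every randomised patient with at least one of the three scores.
- Take the arm difference weighted equally over the three times, and compare its confidence limit with the 1.3 margin.
- Add one sensitivity analysis in which missing Exparel scores are worsened by steps up to the margin. The model relies on misses being explained by the observed data; this tests departures in the direction that matters for non-inferiority.

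The cost is SAP wording and a little programming, with no new patients or data. The small downside is a model-based estimate in place of a plain t-test; with complete data both give the same difference.

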##### 4.1.2 Secondary Endpoints

- 1. NRS pain scores at rest on PACU, POD1, POD2, POD3, POD4, POD7
- 2. NRS pain scores with movement in PACU, POD 1, POD2, POD3, POD4, POD7
- 3. Brief Pain Inventory short-form in PACU, POD1, POD2, POD3, POD4, POD7
- 4. Opioid consumption in PACU, POD1, POD2, POD3, POD4, POD 7
- 5. Patient Satisfaction with pain treatment in PACU, POD 1, POD 2, POD 3, POD 4, POD 7
- 6. Duration of analgesic block via RA phone call 24, 48, 72 hours after block placement (or longer if block continues): Patient's will be asked "Since being discharged, when did you first take an analgesic medication for shoulder pain?" and "When did your pain relief from the block completely wore off?"
- 7. Sensory resolution in PACU, POD1, POD2, POD3, POD4, POD7 (full resolution of block will be reported by the patient via RA phone call 24, 48, 72 hours after block placement or longer if duration continues, "When did your numbness completely resolve and returned to normal?", will likely be until POD 1, but would continue until block resolution)
- 8. Motor block resolution in PACU, POD1, POD2, POD3, POD4, POD7 (full resolution of block will be reported by the patient via RA phone call 24, 48, 72 hours after block placement or longer if block continues, "When did your arm or hand weakness resolve and returned to normal?", will likely be until POD 1, but would continue until block resolution)
- 9. Success of interscalene block: C5 Dermatome distribution will be assessed in the PACU by the anesthesiologist (co-i). Alcohol swab test (2-normal cold sensation, 1-diminished/dull, 0-absence of cold sensation). Motor test: hand grip (normal-2, weak-1, absent-0)
- 10. Adverse effects: sensory-motor deficits: incidence of paresthesia / neuropraxia: persistent tingling, numbness on POD7, if patient reports persistent neuropraxia after POD7, will follow up on POD14. If neuropraxia persists, will notify attending anesthesiologist and continue to

follow until postoperative neurological symptoms (PONS) resolve. On POD 7, patients will be asked “on the side where surgery was performed, do you have any numbness, tingling, or weakness in the hand or fingers?”

- 11. If the response to continued numbness/tingling in fingers on POD7 is yes, adverse effects will be asked on POD 14.
- 12. Incidence of ISB related side effects: Horner’s syndrome, hoarseness, hiccups, dyspnea in PACU, POD1-4,7
- 13. Time to readiness for PACU discharge (time of PACU admission to time of readiness to discharge, measured by Post Anesthetic Discharge Scoring System) evaluated every 15 minutes
- 14. Length of PACU stay (time of PACU admission to PACU discharge)

## 4.2 Study Sites

This study will take place at the main campus of the Hospital for Special Surgery (HSS).

## 5.0 STUDY POPULATION

### 5.1 Number of Subjects

112

### 5.2 Inclusion Criteria

Subjects of either gender will be included if:

1. Scheduled for elective outpatient arthroscopic shoulder surgery
2. ASA I-III
3. Age 18 years or older

### 5.3 Exclusion Criteria

Subjects will be excluded from the study if:

- History of allergy to local anesthetic, or one of the study medications
- Pre-existing neurological deficits
- Psychiatric or cognitive disorders that prohibit patients from following study protocol
- History of drug or alcohol abuse
- Chronic Opioid use (longer than 3 months)
- Chronic pain syndromes
- Infection at the site of injection
- Patients with severe pulmonary disease
- Herniated cervical disc, cervical myelopathy
- Contraindication for general anesthesia and/or interscalene nerve blocks
- Pregnancy
- Open shoulder arthrotomies
- Non-English speakers

## 6.0 PROCEDURES

### 6.1 Intraoperative Protocol

Following sedation, the interscalene block will be done using an ultrasound-guided, in-plane approach. The anesthesiologist will target below the C5 nerve root. A 22 gauge 1.5-2 inch needle is advanced in-plane from lateral medial through the middle scalene muscle until the needle tip is positioned in the interscalene groove between the C5 and C6 nerve roots. Patients will be randomized to two groups:

1. Dexamethasone: 15mL of 0.5% bupivacaine with 4mg of preservative-free dexamethasone will be injected
2. Exparel: 10mL of 133mg liposomal bupivacaine with 5mL of 0.5% bupivacaine (15mL total)

Premedication will consist of 2-5mg of Midazolam. After block induction, general anesthesia will be performed by administration of propofol (induction doses of 2mg/kg) by the anesthesiologist. LMA will be inserted and anesthesia maintained with Propofol infusion and Fentanyl (Fentanyl 25-50mcg titrated up to 200mcg) as needed. To avoid PONV, 4mg Decadron (Dex group) or 8mg Decadron (Exparel group) will be administered, as well as 4mg Zofran for both groups. Before the end of surgery, 15-30mg Ketorolac will be given (30mg for patients under 65 and over 50kg, 15mg for patients under 65 or under 50kg).

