### 6.2 Postoperative Protocol

Postop medication includes IV acetaminophen (1g IV upon PACU arrival, 750mg if <50kg), ketorolac (30mg IV q hours following intraop dose if not yet discharged, 15mg for 65 years or older, <50kg). For pain control, tramadol 50mg q 6 hours PRN (mild pain [1-3]); tramadol 100mg q hours (or 75mg if <50kg) (moderate pain [4-6]); oxycodone 5mg q 3 hours (severe pain [7-10]); dilaudid IV for rescue analgesia. Patients will be discharged with Naproxen 500mg q 12 hours, Percocet 5-325mg 1-2 tabs q 4 hours PRN, and Zofran 8mg q 8 hours.

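### The intraoperative ketorolac rule in section 6.1 gives two doses to one age-and-weight group and none to another, because its 15 mg clause has the age condition the wrong way round

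*Combined protocol and SAP*

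**What the plan says.** Section 6.1 (Intraoperative Protocol) has ketorolac given to every participant before surgery ends: "15-30mg Ketorolac will be given (30mg for patients under 65 and over 50kg, 15mg for patients under 65 or under 50kg".

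Section 6.2 (Postoperative Protocol) continues ketorolac in patients not yet discharged, at 30 mg with a reduced dose described as "15mg for 65 years or older, <50kg". The same section reduces two other drugs by weight: acetaminophen ("1g IV upon PACU arrival, 750mg if <50kg") and the tramadol dose for moderate pain ("or 75mg if <50kg").

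On age, section 5.2 (Inclusion Criteria) requires only "Age 18 years or older". Neither 5.2 nor the exclusions in 5.3 set an upper limit, so patients of 65 and over can enrol.

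**The concern.** A two-level dosing rule should put each patient in exactly one level. In 6.1 the phrase for patients younger than 65 appears in both clauses, and nothing in that parenthesis names patients of 65 or older. Section 6.2 uses the same drug, the same two doses and the same age and weight thresholds, but with the age condition in the opposite direction.

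What is at stake is safe and consistent dosing, together with the ability to judge whether the protocol was followed. The group left without a level is the older, heavier group, to whom 6.2 gives the lower dose. For that group 6.1 offers only the general 15 to 30 mg range, whose upper end 6.2 does not give them. The postoperative dose in 6.2 is timed from the intraoperative one, so the two rules apply in sequence to the same patient and ought to agree.

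**Working it through.** The plan has no figure to reproduce here. The check treats each clause as a logical condition and asks which patients satisfy it.

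**Inputs**

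- 6.1, 30 mg clause: "30mg for patients under 65 and over 50kg", i.e. age < 65 AND weight > 50 kg.
- 6.1, 15 mg clause: "15mg for patients under 65 or under 50kg", i.e. age < 65 OR weight < 50 kg.
- 6.2, 15 mg clause: "15mg for 65 years or older, <50kg", i.e. age ≥ 65 OR weight < 50 kg, taking the comma as 'or'; otherwise 30 mg.
- Proposed 6.1: 30 mg if age < 65 AND weight ≥ 50 kg; 15 mg if age ≥ 65 OR weight < 50 kg.

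**Levels assigned, in mg**

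| Group | 6.1 as written | 6.2 | 6.1 as proposed |
|---|---|---|---|
| < 65, < 50 kg | 15 | 15 | 15 |
| < 65, > 50 kg | 30 and 15 | 30 | 30 |
| ≥ 65, < 50 kg | 15 | 15 | 15 |
| ≥ 65, > 50 kg | none | 15 | 15 |

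Two examples show the two failures. At age 64 and 80 kg, the 30 mg clause is true (64 < 65 and 80 > 50) and so is the 15 mg clause (64 < 65). At age 70 and 80 kg, the 30 mg clause is false (70 is not below 65) and so is the 15 mg clause (70 is not below 65, and 80 is not below 50).

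As written, 6.1 therefore agrees with 6.2 in 2 of 4 groups, the two below 50 kg. With the proposed wording it agrees in 4 of 4.

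**Boundary at exactly 50 kg**

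| Age | 6.1 as written | 6.1, age phrase corrected only | 6.2 | 6.1 as proposed |
|---|---|---|---|---|
| < 65 | 15 | none | 30 | 30 |
| ≥ 65 | none | 15 | 15 | 15 |

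Correcting only the age phrase would leave a patient under 65 at exactly 50 kg without a level: the 30 mg clause needs more than 50 kg and the 15 mg clause needs less. All three weight-based reductions in 6.2 (acetaminophen, ketorolac, tramadol) apply strictly below 50 kg, so putting 50 kg itself in the higher-dose category follows the protocol's own convention.

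**Sensitivity to the comma in 6.2.** If the comma meant 'and', 6.2 would give, in the order of the first table, 30, 30, 15 and 30 mg. Agreement would then be 1 of 4 for 6.1 as written and 2 of 4 for the proposed wording. The overlap and the gap within 6.1 do not depend on this reading.

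**The case against.** The best case against is that this is editorial. The intended rule can be worked out from 6.1 alone: beside a 30 mg clause for younger, heavier patients, a 15 mg clause makes sense only as its complement, and 6.2 points the same way. Every patient stays within a stated range of 15 to 30 mg, and no clause assigns 30 mg to anyone aged 65 or more. The rule is the same in both arms. The comparison with 6.2 also depends on reading its comma as 'or', and it is uneven to correct 6.1 for ambiguity while leaving that comma alone.

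Much of this stands. The point is minor, the intent is recoverable, and the agreement counts are conditional on the 'or' reading, which is the more natural one. What does not follow is that the text can be left. A dosing instruction should be executable as written. Here, adherence cannot be judged for the group with no level, and either dose complies for the group with two. Tidying the comma in 6.2 is sensible, but it is not needed to repair 6.1.

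**Conclusion.** The concern holds. The 15 mg clause of 6.1 has the age condition reversed, and nothing else in the document corrects it. The result is one overlap and one gap among four age-by-weight groups. That finding rests only on the literal wording of 6.1. The agreement with 6.2 in 2 of 4 groups additionally assumes that the comma in 6.2 means 'or'.

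The number of patients affected is unknown, because the documents give no age or weight distribution. This is a minor point of dosing safety and internal consistency. The rule does not differ by arm, and no bias, loss of power or effect on the primary analysis is claimed.

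**What to change.** Subject to clinical confirmation, replace the parenthesis in 6.1 with: *30 mg if aged under 65 and weighing 50 kg or more; 15 mg if aged 65 or older or weighing less than 50 kg.* Both changes are needed: the age phrase removes the overlap and the gap, and the weight phrase covers patients at exactly 50 kg.

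The cost is one parenthesis. Section 6.2 need not change, although replacing its comma with 'or' would put its meaning beyond doubt. Sample size, endpoints and the primary analysis are untouched.

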### 6.2 Postoperative Protocol

Postop medication includes IV acetaminophen (1g IV upon PACU arrival, 750mg if <50kg), ketorolac (30mg IV q hours following intraop dose if not yet discharged, 15mg for 65 years or older, <50kg). For pain control, tramadol 50mg q 6 hours PRN (mild pain [1-3]); tramadol 100mg q hours (or 75mg if <50kg) (moderate pain [4-6]); oxycodone 5mg q 3 hours (severe pain [7-10]); dilaudid IV for rescue analgesia. Patients will be discharged with Naproxen 500mg q 12 hours, Percocet 5-325mg 1-2 tabs q 4 hours PRN, and Zofran 8mg q 8 hours.

